**11.5 Calculation or derivation of pharmacodynamic variable(s) (Not Applicable)**

**11.6 Calculation or derivation of pharmacogenetic variables (Not Applicable)**

**11.7 Calculation or derivation of health economic variables (Not Applicable)**

**12. STATISTICAL METHODS AND SAMPLE SIZE DETERMINATION BY ASTRAZENECA**

Full details of the analyses will be provided in the Statistical Analysis Plan which will be finalised before database lock.

The primary objective of the study is to compare the efficacy of 500 mg fulvestrant with 250 mg fulvestrant in terms of progression free survival, assessed by the primary variable, PFS, as defined in Section 11.1.

A secondary objective of the study is to describe the pharmacokinetic profile of fulvestrant 500mg and fulvestrant 250 mg in postmenopausal women with oestrogen receptor positive advanced breast cancer who have progressed or relapsed on endocrine therapy, using the PK parameters defined in Section 11.4.

The further objective of the study is to compare objective response rate, clinical benefit rate, duration of clinical benefit and duration of response of 500 mg fulvestrant with 250 mg fulvestrant, assessed by the secondary variables, ORR, CBR, DoCB and DoR, as defined in Section 11.1. And also to assess tolerability of fulvestrant 500 mg compared with fulvestrant 250 mg, assessed by adverse events as defined in Section 11.2.

## **12.1 Description of analysis sets**

### **Full Analysis Set (FAS)**

The primary statistical analysis of the efficacy of 500 mg fulvestrant compared to 250 mg fulvestrant will include all randomised patients and will compare the treatment groups on the basis of randomised treatment, regardless of the treatment actually received. Therefore efficacy data will be summarised and analysed on an FAS basis. This approach will be used when assessing progression-free survival, objective response rates, clinical benefit rates, duration of clinical benefit and duration of response.

### **Per protocol (PP)**

In addition, a per protocol (PP) analysis excluding significant protocol violators and deviators will be carried out for the primary variable of PFS using the model with treatment factor only.

### **Pharmacokinetics**

First 30 patients in each arm who consent to the pharmacokinetic(PK) measurements will have pharmacokinetic plasma samples taken. The patients who have actually received the study medication and have evaluable plasma levels of 500 mg fulvestrant and 250 mg fulvestrant will be included for pharmacokinetic analysis.

### **Safety**

When assessing tolerability of 500 mg fulvestrant against 250 mg fulvestrant, safety population, a subset of the FAS population that includes all patients who received at least one dose of study medication will be used to produce summaries based on study treatment actually received.

## **12.2 Methods of statistical analyses**

The primary analysis on the primary variable of PFS will be performed using a stratified log-rank test in the FAS population.

Following a request from the Chinese State Food and Drug Administration(SFDA) to perform subgroup analyses of patients on the basis of the last therapy received prior to fulvestrant (AI vs AO therapy), the randomisation scheme and primary analysis have been stratified to ensure that a similar proportion of post AI and post AO patients are in each treatment group. Section [12.2.6](#) provides further details of the planned subgroup analyses. In addition to the stratified log rank test for PFS based on the FAS population, a Cox regression model will also be performed with factors fitted for treatment and other baseline covariates (adjusted model).

The conclusions will be based on the log rank test analysis as this is considered as the primary analysis. If the log rank test and the adjusted analysis yield different results, the consequence of covariate adjustments will be explored.

A secondary Per Protocol analysis of PFS will be performed using a stratified log-rank test in order to assess the reliability of the conclusions from the primary FAS analysis. For objective

response rate and clinical benefit rate, a logistic regression model will be fitted with treatment factor only. Duration of response and duration of clinical benefit will be summarised using the Kaplan-Meier method.

### **12.2.1 Progression-free Survival**

For the primary analysis of PFS, to assess efficacy of 500 mg fulvestrant against 250 mg fulvestrant, the following analysis will be carried out:

Formal treatment comparisons will be analysed using a stratified log-rank test as a primary method.

In addition, a secondary analysis using the Cox regression model will be performed to investigate any impact of baseline covariates. The following baseline covariates will be fitted in the Cox regression model:

- Age ( $\leq 65$  vs.  $>65$ )
- Response to last endocrine therapy received prior to fulvestrant (responsive / not responsive)
- Receptor status at diagnosis (both ER+ & PgR+ vs. ER+ & PgR other)
- Visceral involvement (Yes/No)
- Last therapy received prior to fulvestrant (Aromatase Inhibitor (AI)/ Anti-Oestrogen(AO))
- Measurable disease (Yes/No)

The effects of centre and treatment by centre interaction will be investigated if possible; however, it is recognised that this investigation may be limited if recruitment at most centres is low, which will cause problems with computational convergence. No analysis will be performed for individual centres or a subgroup of centres.

### **12.2.2 Pharmacokinetics**

All PK parameters will be listed (CL/F, Vss/F etc). Only  $C_{max}$ ,  $t_{max}$ ,  $C_{min}$ ,  $AUC_{0-\tau}$  and  $t_{1/2}$  may be summarised.

### **12.2.3 Objective Response Rate and Clinical Benefit Rate**

Assessments of tumour response will be based on the RECIST 1.1 criteria for patients with measurable disease at baseline.

ORR is defined as the proportion of responders (CR and PR). CBR is defined as the proportion of responders plus those with  $SD \geq 24$  weeks.

Treatment comparison in ORR and CBR will be analysed using a logistic regression model with treatment factor only. Results will be expressed as the odds ratio together with the corresponding 95 % CI and p-value. The estimate of the difference in ORRs (500 mg fulvestrant vs. 250 mg fulvestrant) and the corresponding 2-sided 95% CI will also be presented.

The best objective response of CR, PR, SD $\geq$ 24 weeks, SD<24 weeks, and progression will be summarised.

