- Data from Study CONFIRM ([A Di Leo et al 2009](#)), a phase III randomised parallel-group trial, demonstrated that fulvestrant 500mg offers a statistically significant longer TTP compared with fulvestrant 250mg (median TTP: 6.5 months vs. 5.5 months; hazard ratio=0.80 [95% CI 0.68 to 0.94]; P=0.006), which seemed to be the consequence of an increase in the rate, and of a prolongation in duration, of disease stabilization. The 50% events overall survival analysis also seemed to favour fulvestrant 500mg, although statistical significance was not reached(hazard ratio=0.84 [95% CI 0.69 to 1.03]; P=0.091). The safety analysis did not raise any relevant concerns in relation to fulvestrant 500mg.

Therefore, this study will compare Fulvestrant 500mg with fulvestrant 250mg in a Chinese population in order to understand the optimal dose for Chinese patients with breast cancer.

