### **5.2.1 Procedures for randomisation**

Eligible patients will be randomised in a 1:1 ratio (fulvestrant 500mg : fulvestrant 250mg). The actual treatment given to individual patients will be determined by a randomisation scheme that has been loaded into the Interactive Voice/Web Response System (IVRS/IWRS) database. The randomisation scheme will be produced by a computer software program called GRand (AZ Global Randomisation system) that incorporates a standard procedure for generating random numbers. A biostatistics group at AstraZeneca has responsibility for generating the randomisation scheme.

A blocked randomisation will be generated and all centres will use the same list in order to minimise any imbalance in the number of patients assigned to each treatment group. The randomisation scheme will be stratified by the last therapy received prior to fulvestrant (AI vs AO therapy).

Based on clinical practice in China, it is anticipated that a significant proportion (>40%) of patients will enter the study having progressed/relapsed on an AI. The ratio of post-AI and post-AO patients will be monitored during study recruitment and for consistency with CONFIRM (42.5% post-AI), enrolment of post-AI patients will stop once 100 post-AI patients (45%) have been randomised.

Patient eligibility will be established before treatment randomisation. Patients will be randomised strictly sequentially, as patients are eligible for randomisation. Once the eligibility of a patient has been confirmed, the Investigator (or nominated assistant) should contact the IVRS/IWRS system and follow the procedures as described in the IVRS/IWRS user manual.

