### **12.3 Determination of sample size**

The study will randomised 220 postmenopausal women with oestrogen receptor positive advanced breast cancer and it is expected to obtain at least 100 evaluable postmenopausal women per treatment group so as to meet the SFDA's requirements for registration trials. The 220 patients will be randomised in a 1:1 ratio to fulvestrant 500mg and fulvestrant 250mg. The primary analysis for PFS will be carried out when at least 150 progression events have been observed.

A criterion has been predefined for declaring consistency with CONFIRM. The results of this study would be considered to be consistent with CONFIRM if the hazard ratio point estimate for the treatment comparison is <1 (i.e. if it is in the same direction as in CONFIRM). With a

sample size of 220 randomised patients and 150 progression events, if there is no ethnic difference with the CONFIRM population, there is an 89% chance the HR <1.

For the PK part, no specific statistical hypothesis will be tested. Because of the long apparent  $t_{1/2}$ , intensive sampling for fulvestrant is problematic. For this reason sparse sampling is preferred and has been used in other fulvestrant PK studies ([Pritchard KI et al 2010](#); [Ohno.S et al 2010](#)). The sparse data will be analyzed by a mixed effect compartmental model (not non-compartmental analysis). Based on experience from prior fulvestrant PK studies, this study plans to recruit approximately 30 patients per arm for PK analysis for comparison with existing PK data for fulvestrant. Recruitment into the PK analysis will be on the basis of the first 30 patients per group who consent to the analysis.

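### Per-protocol PFS is specified in two incompatible ways (Sections 12.1 and 12.2); separately and of minor weight, the ORR and CBR comparisons omit the one randomisation stratum

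*Protocol*

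**What the plan says.** On randomisation, Protocol Section 5.2.1 states: "The randomisation scheme will be stratified by the last therapy received prior to fulvestrant (AI vs AO therapy". This is the only stratification factor. Section 12.2 stratifies the primary PFS log-rank test in the FAS, and the synopsis names last therapy as the stratum. The supporting Cox model in Section 12.2.1 includes last therapy among its covariates.

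On per-protocol PFS there are two statements. Section 12.1, under Per protocol, has the analysis done "for the primary variable of PFS using the model with treatment factor only". Section 12.2 states: "A secondary Per Protocol analysis of PFS will be performed using a stratified log-rank test", and gives its purpose as checking how far the primary FAS conclusion can be relied on. The synopsis mentions a per-protocol analysis of PFS but names no method for it.

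On response, Section 12.2.3 states: "Treatment comparison in ORR and CBR will be analysed using a logistic regression model with treatment factor only". The synopsis and Section 12.2 give the same model. Results are an odds ratio with 95% CI and p-value, and for ORR also a difference in rates with a two-sided 95% CI.

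**The concern.** The per-protocol conflict concerns the primary variable, and it is not detail left for the SAP. The protocol fixes two methods, so an SAP that follows one section departs from the other. If Section 12.1 is followed, the FAS and per-protocol results differ in method as well as in population, and a discrepancy between them cannot be attributed to either. Section 12.3 judges consistency with CONFIRM on whether the hazard ratio point estimate is below 1, so it matters to know why two PFS estimates differ.

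For ORR and CBR, the design balances the arms within AI and AO strata, and the analysis then ignores those strata without giving a reason. At stake are a little power for the odds-ratio test and a little precision for the ORR difference.

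**Working it through.** **Per-protocol PFS.** No arithmetic applies. The two statements describe the same analysis of the same variable. Section 12.1 leaves nothing in the model but treatment, and Section 12.2 stratifies by last therapy. The protocol gives no PFS by stratum and arm, so I put no figure on the numerical difference. If last therapy is prognostic, the unstratified hazard ratio tends to lie closer to 1 than the stratified one, so a FAS versus per-protocol difference could arise from method alone.

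**The plan's own figure.** The protocol quantifies nothing on ORR, CBR or the per-protocol analysis. Its one design figure is the 89% chance of HR < 1 in Section 12.3. The inputs are 150 events ("The primary analysis for PFS will be carried out when at least 150 progression events have been observed") and the CONFIRM result ("hazard ratio=0.80 [95% CI 0.68 to 0.94]; P=0.006").
- With the HR fixed at 0.80: Φ(0.2231/√(4/150)) = 91.4%.
- Adding the CONFIRM standard error, (ln 0.94 − ln 0.68)/(2 × 1.96) = 0.0826: Φ(0.2231/√(4/150 + 0.0826²)) = 88.9%.

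The 89% therefore reproduces once that uncertainty is included. It has no bearing on this point.

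**Inputs for ORR and CBR.**
- "The 220 patients will be randomised in a 1:1 ratio to fulvestrant 500mg and fulvestrant 250mg" (Section 12.3), so 110 per arm.
- "enrolment of post-AI patients will stop once 100 post-AI patients (45%) have been randomised" (Section 5.2.1), taken as 100 post-AI and 120 post-AO, that is 50 and 60 per arm.
- Post-AI CBR of 35% (27 of 77, the phase II study described in Section 3.2).
- Assumed, because the protocol gives no value: post-AO CBR of 35% to 65%, and ORR of 5% post-AI and 15% post-AO.

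**Formulas with no treatment effect.** Let T = p̄(1 − p̄) for the pooled rate p̄, and let W be the average of p(1 − p) over strata with weights 100/220 and 120/220. W never exceeds T.
- SE of the log odds ratio: √(2/(110·T)) unadjusted and √(2/(110·W)) adjusted.
- SE of the risk difference: √(2T/110) unadjusted and √(2W/110) stratified.

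The variance term sits in the denominator on the log-odds scale and in the numerator on the difference scale, so adjustment moves the two standard errors in opposite directions.

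Example at 35% and 55%: p̄ = (35 + 66)/220 = 0.4591, T = 0.2483, W = (22.75 + 29.70)/220 = 0.2384. SE(log OR) goes from 0.271 to 0.276. SE(difference) goes from 0.0672 to 0.0658.

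| Endpoint, post-AI / post-AO | SE(log OR), treatment only → adjusted | SE(difference), unstratified → stratified |
|---|---|---|
| CBR 35% / 35% | 0.283 → 0.283 (0%) | 0.0643 → 0.0643 (0%) |
| CBR 35% / 45% | 0.275 → 0.276 (+0.5%) | 0.0662 → 0.0658 (−0.5%) |
| CBR 35% / 55% | 0.271 → 0.276 (+2.1%) | 0.0672 → 0.0658 (−2.0%) |
| CBR 35% / 65% | 0.270 → 0.283 (+4.8%) | 0.0674 → 0.0643 (−4.6%) |
| ORR 5% / 15% | 0.441 → 0.447 (+1.4%) | 0.0413 → 0.0407 (−1.3%) |

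The plan asks for a difference only for ORR; the CBR differences are shown for scale. ORR covers only patients with measurable disease. Taking 150 such patients leaves the ratios unchanged.

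**Why power can still rise.** The adjusted odds ratio lies further from 1. With a within-stratum odds ratio of 1.5 at 35% and 65%, the marginal odds ratio is 1.447. Then z = ln 1.447/0.2728 = 1.355 unadjusted and ln 1.5/0.2862 = 1.417 adjusted.

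**Simulation** (4,000 trials per scenario, 50 post-AI and 60 post-AO per arm). Adjusted intervals for the log odds ratio were 1.002 to 1.055 times as wide as unadjusted ones. Rejection at an odds ratio of 1.0 was 0.042 to 0.050 unadjusted and 0.044 to 0.054 adjusted. CBR power at an odds ratio of 1.8:

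| Post-AO CBR | Treatment only | Adjusted |
|---|---|---|
| 35% | 0.569 | 0.569 |
| 45% | 0.573 | 0.574 |
| 55% | 0.537 | 0.544 |
| 65% | 0.492 | 0.538 |

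The Monte Carlo standard error of each power figure is at most √(0.25/4000) = 0.008.

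**The case against.** On per-protocol PFS, one can say that the analysis is only supportive and that Section 12.2, the methods section, already gives the matching method. One can also say that a stratified log-rank test has treatment as its only factor, with the strata not counted as factors. The first argument limits the weight of the point. The second is a possible reading, but the protocol nowhere states it. Section 12.2 uses the language of fitted factors for the Cox model, and Section 12.2.1 lists last therapy there as a covariate, so a model with treatment alone reads most naturally as one without last therapy. The two sections still need reconciling.

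On ORR and CBR the opposing case is stronger. The model is prespecified, and the synopsis, Section 12.2 and Section 12.2.3 agree on it. A marginal odds ratio is a legitimate summary for secondary endpoints, and the trial's conclusions rest on the PFS log-rank test. Adding last therapy also changes what the odds ratio estimates. All of this stands, and it is why this part is minor.

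A reader might infer that leaving out the stratum makes the odds-ratio intervals needlessly wide. That is wrong for the model specified: the odds ratio is non-collapsible, and adjustment leaves its interval the same or slightly wider. The narrowing argument applies only to the risk difference. A reader might also infer that the ORR and CBR model contradicts Section 12.2. It does not; the contradiction concerns per-protocol PFS alone.

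**Conclusion.** Per-protocol PFS is specified in two ways that cannot both be followed, and this should be corrected. It does not affect the primary analysis.

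The ORR and CBR omission is a small loss of efficiency, not an error of validity: the treatment-only test rejected in 4.2% to 5.0% of simulated null trials. Adding last therapy brings about 0 to 5 points of power for CBR at an odds ratio of 1.8. The upper end needs an assumed 30-point gap between the post-AI and post-AO rates; at a 10-point gap the gain is 0.1 points. A stratified risk difference has an interval 0 to about 5% narrower, and about 1% narrower for the ORR difference at 5% and 15%. Only the 35% post-AI CBR comes from the protocol. The other rates, the full 100/120 split and equal arms within strata are assumptions.

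**What to change.** 1. In Section 12.1, under Per protocol, replace the treatment-only wording with: *stratified log-rank test, as in the primary analysis*. Only the analysis set then differs from the primary analysis.
2. In the synopsis and Sections 12.2 and 12.2.3, add last therapy (AI or AO, as randomised) to the ORR and CBR logistic models.
3. In Section 12.2.3, give the ORR difference as a stratum-weighted (Mantel-Haenszel) difference with its 95% CI.

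The first change costs one phrase. The second and third need one two-level factor that the randomisation system already holds. Their real cost is interpretive: the odds ratio becomes conditional on last therapy, and its interval may be slightly wider. The unadjusted odds ratio can be kept as a supportive result.

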#### **12.2.4 Duration of Response and Duration of Clinical Benefit**

Duration of response and duration of clinical benefit will be summarised using the Kaplan-Meier method by randomised treatment. Kaplan-Meier plots and Kaplan-Meier estimates of median DoR and DoCB will be presented for each treatment.

#### **12.2.5 Tolerability**

AE and lab variables will be summarised by treatment actually received. AE data will be summarised in MedDRA by preferred term and system organ class. The number of patients who withdraw or die due to AEs will be summarised.

#### **12.2.6 Subgroup analysis**

A subgroup analysis based on FAS will be performed for subgroup patients of last therapy prior to fulvestrant (AI vs AO therapy) for the variable of PFS at the request of the SFDA. The same analysis as detailed in Section 12.2 will be performed on this subgroup with only treatment factor fitted to the models. No adjustment for other covariates will be made.

The subgroup analysis will be exploratory in nature as the study is not appropriately powered to perform a formal subgroup analysis. Consequently, any results obtained from this analysis should be interpreted with caution.

#### **12.2.7 Interim analyses**

No interim analysis will be performed for this trial.

### **12.3 Determination of sample size**

The study will randomised 220 postmenopausal women with oestrogen receptor positive advanced breast cancer and it is expected to obtain at least 100 evaluable postmenopausal women per treatment group so as to meet the SFDA's requirements for registration trials. The 220 patients will be randomised in a 1:1 ratio to fulvestrant 500mg and fulvestrant 250mg. The primary analysis for PFS will be carried out when at least 150 progression events have been observed.

A criterion has been predefined for declaring consistency with CONFIRM. The results of this study would be considered to be consistent with CONFIRM if the hazard ratio point estimate for the treatment comparison is <1 (i.e. if it is in the same direction as in CONFIRM). With a

sample size of 220 randomised patients and 150 progression events, if there is no ethnic difference with the CONFIRM population, there is an 89% chance the HR <1.

For the PK part, no specific statistical hypothesis will be tested. Because of the long apparent  $t_{1/2}$ , intensive sampling for fulvestrant is problematic. For this reason sparse sampling is preferred and has been used in other fulvestrant PK studies ([Pritchard KI et al 2010](#); [Ohno.S et al 2010](#)). The sparse data will be analyzed by a mixed effect compartmental model (not non-compartmental analysis). Based on experience from prior fulvestrant PK studies, this study plans to recruit approximately 30 patients per arm for PK analysis for comparison with existing PK data for fulvestrant. Recruitment into the PK analysis will be on the basis of the first 30 patients per group who consent to the analysis.

#### **12.4 Data monitoring committee**

No data monitoring committee will be used in this study.

## 13. IMPORTANT MEDICAL PROCEDURES TO BE FOLLOWED BY THE INVESTIGATOR

### 13.1 Medical emergencies and AstraZeneca contacts

The Principal Investigator is responsible for ensuring that procedures and expertise are available to handle medical emergencies during the study. **A medical emergency usually constitutes an SAE and is to be reported as such, see Section 6.4.4.**

In the case of a medical emergency the investigator may contact the Study Delivery Team Leader. If the Study Delivery Team Leader is not available, contact the Study Delivery Team Physician at the AstraZeneca Research and Development site shown below.

Name	Role in the study	Address & telephone number

### 13.2 Overdose

An overdose is defined as a dose administered to a patient that is in excess of the randomised dose for patients.

- An overdose with associated AEs is recorded as the AE diagnosis/symptoms on the relevant AE modules in the CRF and on the Overdose CRF module.
- An overdose without associated symptoms is only reported on the Overdose CRF module.

If an overdose on an AstraZeneca study drug occurs in the course of the study, then investigators or other site personnel inform appropriate AstraZeneca representatives **within one day**, ie, immediately but no later than **the end of the next business day** of when he or she becomes aware of it.

The designated AstraZeneca representative works with the investigator to ensure that all relevant information is provided to the AstraZeneca Patient Safety data entry site.

For overdoses associated with SAE, the designated AstraZeneca representative works with the investigator to ensure that all the necessary information is provided to the AstraZeneca Patient Safety data entry site within 1 calendar day of initial receipt for fatal or life threatening events and within 4 calendar days of initial receipt for all other SAEs. For other overdoses (i.e. without symptoms or with non-serious adverse events) reporting to the Patient Safety data entry site should be done within 5 calendar days.

For fulvestrant, there is no human experience of overdosage to date. Animal studies suggest that no effects other than those related directly or indirectly to antioestrogenic activity were evident with higher doses of fulvestrant. Thus, it indicates that overdose should be managed symptomatically.

